## **9. Funding and Conflicts of Interest**

This study is investigator-initiated and self-funded. All study-related activities, including patient recruitment, data collection, follow-up, and statistical analysis, are carried out using the resources of the research team at the Bach Mai Hospital. No external funding or sponsorship has been obtained from pharmaceutical companies, academic institutions, or governmental agencies.

The investigators declare no conflicts of interest. There are no financial, institutional, or personal relationships that could be perceived to influence the design, conduct, interpretation, or publication of this study.

## **10. Administrative Aspects, Monitoring, and Publication**

### **10.1. Study Administration**

The study is conducted under the supervision of Bach Mai Hospital. A designated principal investigator is responsible for overall coordination, compliance with the protocol, and ensuring data quality. Study procedures are implemented in accordance with the approved protocol, Good Clinical Practice (GCP), and local regulatory requirements.

### **10.2. Data Management and Monitoring**

Study data will be collected and stored in a secure, password-protected electronic database. Data entry will be performed by trained personnel and subject to regular quality

control checks. The study team will periodically monitor data for completeness, consistency, and adherence to the study protocol. No formal external monitoring or auditing is planned, given the observational and non-interventional nature of the study.

### **10.3. Confidentiality**

Patient confidentiality will be strictly maintained. All data will be de-identified and coded using unique study identifiers. Access to identifiable patient information will be restricted to authorized personnel only.

### **10.4. Protocol Amendments**

Any significant changes to the study protocol will be documented, submitted for ethical approval, and communicated to all relevant parties, including the study registry if applicable.

### **10.5. Publication Policy**

The results of the study will be disseminated through scientific publications and conference presentations. Authorship will follow the criteria established by the International Committee of Medical Journal Editors (ICMJE). The research team is committed to transparency and will ensure that study findings are made publicly accessible regardless of outcome.

## APPENDIX A.

### Standard Operating Procedure for the Scoring of Cerebral Venous Recanalization

#### Objective

Imaging Modalities Accepted

- Magnetic resonance venography (MRV)
- Computed tomography venography (CTV)
- Digital subtraction angiography (DSA), if available

Grade	Definition
0	No recanalization: Persistent occlusion with no visible flow.
1	Partial recanalization: Incomplete restoration of venous flow.
2	Complete recanalization: Full restoration of flow with no residual occlusion.

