## **5.2. Study procedures**

Baseline clinical and radiological data, including patient demographics, risk factors, imaging findings, anticoagulant treatment details, and in-hospital events during the acute phase of CVT, will be collected for all enrolled patients.

Participants will be followed up at 3 and 6 months after diagnosis. Data collected at these time points will include:

- Type and duration of oral anticoagulant therapy
- Clinical events, including recurrent thrombotic or bleeding events
- Degree of disability will be assessed using mRS
- Venous recanalization will be assessed at 6 months using brain MRI with venography or CT venography. Recanalization will be categorized as complete, partial, or none, based on the classification proposed by Aguiar de Sousa et al
- Health-related quality of life, evaluated using the EQ-5D-5L instrument. This tool evaluates five domains (mobility, self-care, usual activities, pain/discomfort, and anxiety/depression), each with five levels of severity. A utility index score will be calculated using the Vietnamese EQ-5D-5L value set, ranging from -0.511 to 1.000, where 1.000 indicates perfect health, 0.000 corresponds to death, scores below 0 indicate health states considered worse than death by the general Vietnamese population.
- Presence of chronic headache, defined as a headache occurring on  $\geq 15$  days per month and persisting for more than 3 months following the acute CVT event, consistent with the International Classification of Headache Disorders, 3rd edition

(ICHD-3). Headache-related disability, assessed using the Headache Impact Test (HIT-6)

All data will be collected as part of routine clinical care during outpatient visits or structured telephone interviews and recorded using standardized case report forms.

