## **6. STATISTICAL ANALYSES**

All statistical analyses will be conducted using R software (version 4.4.1). Statistical significance will be set at a two-sided p-value < 0.05.

Descriptive statistics will be used to summarize baseline characteristics. Continuous variables will be reported as means  $\pm$  standard deviations (SD) or medians with interquartile ranges (IQR), depending on distribution. Categorical variables will be expressed as counts and percentages.

The primary endpoint: a composite of major bleeding (per ISTH criteria) or symptomatic recurrent venous thromboembolism (VTE), including cerebral venous thrombosis, deep vein thrombosis, pulmonary embolism, or splanchnic vein thrombosis—will be analyzed as a time-to-event outcome. Kaplan–Meier survival curves will be constructed, and group comparisons will be performed using the log-rank test. Cumulative event rates at 6 months will be reported with 95% confidence intervals.

For secondary endpoints, the following analyses will be conducted:

- Functional outcome (mRS 0-1 vs 2-6 at 3 and 6 months) will be analyzed using logistic regression to identify predictors of favorable recovery.

- Venous recanalization status at 6 months will be described as complete, partial, or absent, based on follow-up imaging, and summarized as proportions.
- Rates of major bleeding, any bleeding, symptomatic recurrent VTE, and arterial thrombotic events will be summarized descriptively and reported with 95% confidence intervals.
- Health-related quality of life (EQ-5D-5L), chronic post-CVT headache (HIT-6), at 3 and 6 months will be compared using paired t-tests or Wilcoxon signed-rank tests, as appropriate.
- Changes in D-dimer levels from baseline to follow-up will be analyzed using paired tests and visualized longitudinally.

Missing data will be handled using complete case analysis. If the missing rate exceeds 10% for any variable, sensitivity analyses will be performed.

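### Appendix A's recanalization grades fit only veins fully occluded at baseline, so an unchanged non-occlusive thrombus cannot be graded as none and worsening has no grade of its own

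*Protocol*

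**What the plan says.** Venous recanalization at 6 months is a secondary endpoint (Protocol Sections 2 and 5.1.2).

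- **Categories (Section 5.2).** "Recanalization will be categorized as complete, partial, or none", with reference to a published classification.
- **Grades (Appendix A, the scoring procedure).** Grade 0 is "No recanalization: Persistent occlusion with no visible flow". Grade 1 is "Partial recanalization: Incomplete restoration of venous flow". Grade 2 is "Complete recanalization: Full restoration of flow with no residual occlusion".
- **Analysis (Section 6).** "Venous recanalization status at 6 months will be described as complete, partial, or absent, based on follow-up imaging, and summarized as proportions". No test, comparator or threshold is attached.
- **Eligibility (Section 4.2).** CVT must be confirmed by the clinical picture and by venography or DSA with MRI or CT. Neither the inclusion nor the exclusion criteria mention whether the thrombus occludes the vein.
- **Baseline imaging (Section 5.2).** Collected for all patients: "Baseline clinical and radiological data, including patient demographics, risk factors, imaging findings, anticoagulant treatment details". Nothing links these findings to the 6-month score.

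**The concern.** Recanalization is a change from baseline. The three grades describe that change properly only when the vein had no flow to begin with: an occlusion that persists, flow that partly returns, flow that fully returns. The eligibility criteria also let in patients whose thrombus left some flow, and for them the scale has no place for no change or for deterioration.

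At stake is the meaning of two of the three reported proportions. If such patients are put in grade 1 by default, the partial category contains patients in whom nothing reopened, and the none category is too small. If readers handle the case differently, the grades are not reproducible. An analysis plan cannot repair this later, because the missing information is the comparison with baseline that the reader was never told to record. It would take a second reading of the scans.

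**Working it through.** The plan states no figure on this point, so there is none to reproduce. The check is whether every possible course from baseline to 6 months has a grade.

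**Step 1: the grades against eight courses.** Two ways of reading Appendix A are applied: (a) the words taken strictly, so that grade 0 needs an occlusion that has persisted and grades 1 and 2 need flow that has been restored; (b) only the flow visible at 6 months, so that no flow = 0, some flow = 1, full flow = 2.

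| Baseline | 6 months | (a) Strict wording | (b) Visible flow only |
|---|---|---|---|
| Occlusive | Still occluded | 0 | 0 |
| Occlusive | Some flow | 1 | 1 |
| Occlusive | Open | 2 | 2 |
| Non-occlusive | Unchanged | no grade | 1 |
| Non-occlusive | Improved, residual thrombus | 1 | 1 |
| Non-occlusive | Open | 2 | 2 |
| Non-occlusive | Worse, some flow left | no grade | 1 |
| Non-occlusive | Now occluded | no grade | 0 |

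All occlusive courses, and the non-occlusive ones that improve, are graded correctly either way. The other three are not. Under (a) they have no grade. Under (b) unchanged and worse-with-flow both count as partial recanalization, and a new occlusion is merged with an old one that never opened. Neither reading gives the unchanged patient the grade for no recanalization.

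**Step 2: which proportions move.** None of the three problem courses belongs in grade 2 or is put there. The complete share is therefore unaffected, provided these patients stay in the denominator. What moves is the split between none and partial.

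**Step 3: illustrative size.** The documents give no share of non-occlusive thrombus and no share unchanged, so both are assumptions. N = 69 is the planned minimum (Section 5.3).

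Patients affected = N × share non-occlusive × share of those unchanged

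- Low: 69 × 0.10 × 0.20 = 1.4 (0.10 × 0.20 = 2 percentage points)
- High: 69 × 0.30 × 0.40 = 8.3 (0.30 × 0.40 = 12 percentage points)
- Other assumptions, 10-50% non-occlusive and 10-30% unchanged: 69 × 0.10 × 0.10 = 0.7 to 69 × 0.50 × 0.30 = 10.3 (1 to 15 percentage points)

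For scale, the 95% confidence half-width for a proportion of 0.5 with N = 69 is 1.96 × √(0.25/69) = 0.118, or 11.8 percentage points. The shift could be trivial or about as large as the sampling error, depending on rates the protocol does not give.

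**The case against.** The case for leaving the text alone has several parts, and much of it stands.

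- **Comparison is implied.** A reader might infer that scoring uses the follow-up scan alone. The protocol does not say so. Section 6 may only be naming the 6-month scan as the data source, and the words persistent and restoration make no sense without a baseline. This stands: what is missing is an explicit comparison step. But supplying the comparison does not rescue the scale, because column (a) then leaves three courses without a grade.
- **Worsening.** A reader might infer that a worse thrombus has no grade at all. That holds only on the strict wording. On visible flow it is graded 0 or 1. The accurate statement is that it cannot be told apart. A recurrent CVT can also be captured in the primary endpoint, although Section 6 restricts that to symptomatic events.
- **Several sinuses.** A patient with one sinus reopened and another still closed might seem to fit grades 0 and 1 equally. Grade 0 requires no visible flow, so grade 1 is the natural patient-level reading. Only the scoring unit and the patient-level rule are unstated.
- **Bias towards DOACs.** This might be inferred from the direction of the shift, but the endpoint is described in DOAC patients without a comparator, and the protocol reports three categories, not any recanalization against none. No treatment comparison is distorted.
- **The cited classification.** It may cover these cases, but it was not available for this review. The Objective heading in Appendix A also has no text beneath it in the copy read. Both limit how firmly one can say that the rule is absent everywhere. They do not change what the grade definitions in Appendix A say.

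**Conclusion.** The point holds in limited form. Appendix A's grades fit veins that were fully occluded at baseline, eligibility does not require occlusion, and no step directs the reader to the baseline venogram. An unchanged non-occlusive thrombus cannot be graded as no recanalization, and worsening is not identifiable. This follows from the wording and needs no outside data.

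Its reach is one descriptive secondary endpoint, and within it the none/partial split. The primary endpoint and the sample size are untouched. The size is unknown: about 1 to 8 of 69 patients under the first set of assumptions, which have no basis in the documents and also suppose that all 69 are imaged, whereas Section 8 expects some missing scans. These figures show that the effect need not be negligible; they do not show that it is large.

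**What to change.** **Appendix A.** Score each sinus or vein thrombosed at baseline against the baseline venogram:

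- Grade 0: no improvement from baseline, whether the thrombus was occlusive or not.
- Grade 1: improved, with residual thrombus.
- Grade 2: fully open.
- Record separately any worsening and any newly involved segment.

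State the patient-level rule: complete only if every baseline segment is complete, none if no segment improved, otherwise partial.

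**Section 6.** Say that status is based on follow-up compared with baseline imaging.

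**Cost.** One appendix and one phrase. No new procedure is needed, since venography or DSA is already part of entry and baseline imaging findings are already collected. Each reading takes slightly longer, and baseline scans of referred patients may have to be retrieved. If the revised grades depart from the classification cited in Section 5.2, the protocol should say so. The change is cheapest before many 6-month scans have been read, because afterwards they must be graded again.

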## APPENDIX B.

### ISTH Definitions of Major and Clinically Relevant Non-Major Bleeding

#### ***Major Bleeding***

Defined according to the International Society on Thrombosis and Haemostasis (ISTH) criteria as any of the following:

- Fatal bleeding
- Symptomatic bleeding in a critical area or organ (e.g., intracranial, intraspinal, intraocular, pericardial, intra-articular, intramuscular with compartment syndrome, or retroperitoneal)
- Bleeding causing a fall in hemoglobin of  $\geq 2$  g/dL
- Bleeding leading to transfusion of  $\geq 2$  units of whole blood or red cells

#### ***Clinically Relevant Non-Major Bleeding***

As per ISTH SSC definition: Bleeding that does not meet the criteria for major bleeding AND is associated with one or more of the following:

- Requires medical intervention by a healthcare professional
- Leads to unscheduled contact with a physician (visit or telephone)
- Results in temporary cessation of anticoagulation therapy
- Causes discomfort or impairment of activities of daily living
